##### Inclusion criteria:

- Must have an acute intestinal condition, based on their ICD-10 codes and OPSC-4 codes
- Must be  $\geq 16$  years of age at the time of admission
- Have at least one full set of vital signs recorded on the day of admission
- Have at least one full set of routine blood tests recorded on the day of admission

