Study Participants	
Data will be derived from electronic patient records collected as part of routine clinical patient care on all general adult wards (excluding maternity) between 2013 and 2020.
 
Inclusion criteria:
 
 
• Must have an acute intestinal condition, based on their ICD-10 codes and OPSC-4 codes
 
• Must be <math>\geq 16</math> years of age at the time of admission
 
• Have at least one full set of vital signs recorded on the day of admission
 
• Have at least one full set of routine blood tests recorded on the day of admission
 
 
Exclusion criteria:
 
 
• Maternity admissions during/after pregnancy
 
• Patients admitted or undergoing abdominal surgery for a second time or more
 
 
Using OPCS-4 codes from PAS and TheatreMan™ and NELA data, we will then identify patients who had an emergency laparotomy, and those who had a laparoscopic procedure. We aim to identify a further group where treatment is futile, suggesting that an early focus on end of life care might be appropriate.

Planned Sample Size	2,500
Follow-up duration	1 year (retrospectively)

Planned Study Period	01 Dec 2020 – 31 May 2021
Primary Objective	Provide mortality rates for different treatment options, and analysis of short- and long-term outcomes.
Secondary Objectives	Define patient sub-groups with similar health characteristics based on clinical data and an established risk index.  Use statistical analysis to predict the risk of death for each patient group and treatment option, which will allow us to identify the best care pathways for each cluster.
Primary Endpoint	Mortality risk for each treatment group
Secondary Endpoints	Risk of other outcomes and long-term complications and association between patient factors and these outcomes
Intervention (s)	N/A

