### **6.2 Objectives**

1. Identify all patients with a condition that would qualify them for emergency abdominal surgery, both laparotomy and keyhole (laparoscopic) procedures, regardless of whether they had surgery

or not. This will be done by filtering electronic hospital records for appropriate diagnosis and operation codes.

2. Provide updated estimates of the average risk of death for different treatment options, including surgical and non-surgical intervention, using statistical analysis of short-term and long-term outcomes. Describe health characteristics of the typical patient population receiving one of the treatment options, based on their clinical data and an established risk index.
3. Logistic regression will be used to predict the risk of death for each patient group and each treatment option, which will allow identification of the best care pathways given a patient's health characteristics.
4. Identify patients who would have likely benefited from a different care pathway than the one they received, using machine learning classification algorithms

Our analysis will form the foundation for the establishment of four well-defined care pathway options, each with the patient's best interest in mind: laparotomy, laparoscopy, other alternative treatment, and end of life care.

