#### **7.4 Study cohort**

Data will be derived from electronic patient records collected as part of routine clinical patient care on all general adult wards (excluding maternity) between 2013 (beginning of NELA and collection of data of interest) and 2020.

All patients with a condition that would qualify them for emergency abdominal surgery will be identified, using their ICD-10 diagnosis and OPSC-4 procedure codes which are part of the electronic patient record. Once patients have been identified, they will be screened against the inclusion/exclusion criteria (see below). For each patient, this will include only the first intervention within the study period in the analysis. Subsequent admissions with an abdominal condition or subsequent interventions will be classified as complication and therefore considered as an outcome.

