### 10.2 Data analysis

Extracted data will be cleaned and quality controlled prior to analysis to ensure all relevant patients have been extracted. Given that our analysis will use only routinely collected, clinical data, missing values are unlikely to pose an issue. Initial analysis of 2018 data confirmed that clinical data within 24h of admission was almost fully complete for a remarkable >97% of admissions, meaning there is likely no need to impute data. We will test whether excluding admissions with missing data will introduce bias.

Our analysis can be broken down into the following steps:

- Comparison of the four treatment groups based on demographics, outcomes and medical pathway. This will include calculating mortality and long-term complication rates (Objective 2).
- Construct and compare risk models for each treatment group to predict short-term and long-term risk and to investigate the effect of both patient and hospital-level factors on outcome (Objective 3).

- Identify patients in each group who are abnormal for the group and might have fared better with a different treatment, using clustering algorithms (Objective 4).

After splitting the data set into subsets for each of the four patient groups using diagnosis and procedure codes (see above), mortality and long-term complication rates will be calculated for each group. Longer-term follow-up will include rates of re-admission to hospital, additional theatre visits and development of new medical conditions, within one year of initial admission with an abdominal emergency. Results will provide updated estimates of the average risks of different surgical procedures as well as the risk of not having surgery. Results will be compared with P-POSSUM mortality. Patient groups will further be characterised the using patient factors. Parameters of interest will include but are not limited to age, sex, mortality, long-term complication rates, admission early warning scores (NEWS, LDTEWS and LDTEWS:NEWS), frailty, medical history (previous ICD-10 codes).

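### Procedure codes help decide who enters the cohort and also assign treatment group, so the entry rule can depend on the treatment being compared; the size and direction of any bias are unknown.

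*Protocol*

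**What the plan says.** Four places in the protocol describe how patients get into the cohort, and all four involve procedure codes.

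- Inclusion criteria (section 7.4, same wording in the synopsis): "Must have an acute intestinal condition, based on their ICD-10 codes and OPSC-4 codes". OPCS-4 is meant.
- Section 7.4, identification before screening: "All patients with a condition that would qualify them for emergency abdominal surgery will be identified, using their ICD-10 diagnosis and OPSC-4 procedure codes".
- Section 6.2, Objective 1: "This will be done by filtering electronic hospital records for appropriate diagnosis and operation codes". The same objective wants patients found "regardless of whether they had surgery" or not.

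Treatment group is assigned from the same kind of code. After the criteria, the synopsis says that, from OPCS-4 codes and theatre and NELA data, "we will then identify patients who had an emergency laparotomy, and those who had a laparoscopic procedure". Section 10.2 begins the group analysis "After splitting the data set into subsets for each of the four patient groups using diagnosis and procedure codes".

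No section says whether the two code systems must both be met, whether either suffices, or whether diagnosis governs entry and procedure only the grouping.

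**The concern.** A procedure code records what was done to the patient, not what the patient had. In this study, what was done is the exposure. If a procedure code can help establish the qualifying condition, eligibility is no longer independent of treatment.

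The primary endpoint is mortality risk by treatment group, and the results are meant to identify lower-risk options and inform care pathways. Those uses need groups drawn from one population of patients with the same kind of condition. If operated patients can come in by a route closed to unoperated patients, part of a mortality difference may reflect the entry rule.

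The analysis in section 10.2 would not remove this. It compares groups with unadjusted tests and then fits a separate logistic model within each treatment group. Diagnosis is a possible risk factor (section 10.1), but a model fitted inside one group cannot correct a difference between groups in who was admitted to the data set.

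**Working it through.** **Inputs (section 8, 2018 pilot).** 901 patients with an abdominal emergency; 530 with laparotomy or laparoscopy; 23 in-hospital deaths with surgery and 28 without; study period 6.5 years.

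**Reproducing the protocol's figures.**
- Surgical share: 530/901 = 58.8% (stated 59%). Non-surgical: 901 − 530 = 371 (41.2%).
- Scaled: 901 × 6.5 = 5,856.5 (stated over 5,800); 530 × 6.5 = 3,445 (stated over 3,400).
- Mortality: 23/530 = 4.34% (stated 4.3%); 28/371 = 7.55% (stated 7.6%, a rounding-level difference). Gap: 3.21 points.

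**Reading 1: both codes required.** If a qualifying operation is needed, only 530 a year qualify, or 3,445 over the period. The other 371 × 6.5 = 2,411.5 patients, and about 28 × 6.5 = 182 deaths, would fall outside. This conflicts with the projected 5,800 and with Objective 1. It is an upper bound, because OPCS-4 also covers non-operative procedures and some of the 371 may carry such a code, for example for interventional radiology.

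**Reading 2: either code suffices.** The 901 stand, but the routes differ:

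| | Listed diagnosis only | Procedure code only |
|---|---|---|
| Operated patient | enters | may enter |
| Patient with no procedure | enters | route not available |

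**What reading 2 could do to the result (assumptions only).** Let f be the share of the 530 who entered on a procedure code alone, and q their mortality. Neither is in the protocol. With m = 4.34%, surgical mortality among those with a listed diagnosis is (m − f·q)/(1 − f). Cohort size under a diagnosis-only rule is [530(1 − f) + 371] × 6.5.

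| f (assumed) | Cohort, 6.5 years | Surgical share | q = 0 | q = m | q = 2m |
|---|---|---|---|---|---|
| 0% | 5,857 | 58.8% | 4.34% | 4.34% | 4.34% |
| 5% | 5,684 | 57.6% | 4.57% | 4.34% | 4.11% |
| 10% | 5,512 | 56.3% | 4.82% | 4.34% | 3.86% |
| 20% | 5,168 | 53.3% | 5.42% | 4.34% | 3.25% |

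At f = 20%, the gap to the non-surgical 7.55% would be 2.12 points if none of these patients died, 3.21 if they died at the surgical average, and 4.29 if they died at twice that rate. At f = 0 nothing changes. The direction depends on q.

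**The case against.** The strongest reply is that the authors meant diagnosis to govern entry and procedure codes to do the sorting. Section 8 describes the cohort in terms of patients diagnosed with an intestinal emergency, and the synopsis places the identification of laparotomy and laparoscopy after the criteria. On that reading the problem disappears. It is a plausible intention, but it is not what the text says: the synopsis, section 6.2 and both parts of section 7.4 name procedure codes in the entry step itself.

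A second reply is that the criterion requires an acute intestinal condition and codes are only the means of establishing it, so a procedure code unrelated to bowel pathology need not qualify. That is fair as far as it goes. No code list is shown, and such a list may properly sit outside the protocol. Its absence is not the complaint. Which code system decides eligibility is already fixed in the inclusion criteria, and that is the point at issue.

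A reader might infer that about 41% of the cohort will be lost. The documents do not support this: the pilot found 371 non-surgical patients, so the strict reading was evidently not applied. A reader might also infer that surgical mortality is diluted by a known amount. That does not follow either, because the table spans no change and both directions.

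It also stands that a diagnosis-only rule has a price. It can miss operated patients whose coded diagnosis is not on the list, although the study wants all abdominal emergencies.

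**Conclusion.** The point holds as a defect in the eligibility rule and should be corrected. Four statements of cohort entry rely partly on procedure codes, and the same kind of code defines the groups compared. The literal reading contradicts Objective 1 and the pilot counts; the permissive reading lets the entry rule differ by treatment.

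The effect on mortality by treatment group cannot be sized. The number of operated patients without a qualifying diagnosis is not given, nor are their outcomes, and the bias may be nil. The mortality figures in the check are illustrations under assumed f and q and should not be quoted as estimates of bias. The count of 371 a year is only a ceiling on what the literal wording would exclude.

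**What to change.** In the synopsis, Objective 1 in section 6.2, and the identification text and inclusion criteria in section 7.4:

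1. Define entry to the treatment comparison by one ICD-10 diagnosis list, applied identically to every patient at the index admission. Section 7.4 now says that for each patient "this will include only the first intervention within the study period in the analysis"; an untreated patient has no such event, so that sentence should be tied to the index admission too.
2. Use OPCS-4, TheatreMan and NELA data only afterwards, to assign treatment group.
3. Report the number and outcomes of operated patients without a listed diagnosis separately, and add a sensitivity analysis that includes them. This supplies the f and q that are now unknown.

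If diagnosis-based entry was intended all along, the correction is one of wording. Otherwise it also needs a changed extraction query, which is modest work in retrospective data. The downside is a somewhat smaller surgical group in the main comparison: 530 × 10% = 53 patients a year if, for example, 10% lacked a listed diagnosis. The sensitivity analysis keeps those patients in view.

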This study will benefit patients by providing information on the outcomes for ALL patients admitted with an intestinal emergency. Effective alternatives to laparotomy exist, including keyhole (laparoscopic) surgery (8-12) and interventional radiology procedures (13-16). These are less invasive and could carry lower risks than a laparotomy. By identifying groups of patients for whom these less invasive procedures may be more appropriate, the development of new alternative care pathways for them can be prioritised. There will sadly be some patients for whom active treatment is futile, such as those with loss of blood supply to the bowel or advanced cancer (17). Defining this patient group too will facilitate the development of pathways that have an earlier focus on symptomatic best end of life care. The characteristics of patients and their outcomes undergoing all the above 4 options will be investigated. Knowing these risks will help us better inform patients of the likely outcomes of their choices.

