### 4.2 Why is this important?

Patients who do have a laparotomy are high risk, with a 10% mortality rate at 30 days measured nationally. This group is closely scrutinised by the National Emergency Laparotomy Audit (NELA) who set strict standards of care, and outcomes from surgery are well characterised (1, 2, 4-6). However, there is clear evidence that patients with intestinal emergencies who do NOT have emergency abdominal surgery (laparotomy) do very poorly, with only 30% of patients surviving to a year from admission (7). Our concern is that patients not undergoing laparotomy, but with the same life-threatening pathology, are being forgotten and do not receive the focus of care that they deserve. To improve the quality of care for these patients, better understand the risk of mortality and associated patient factors for ALL patients admitted with an intestinal emergency is needed.

This much-needed study will benefit patients by providing information on the 30-day and 1-year mortality for all patients with an intestinal emergency admitted to our hospital over a 6.5-year period. By observing relationships between mortality and patient factors like age, diagnosis, co-morbidities, vital signs, blood tests and surgery versus no-surgery, factors influencing patient outcomes will be identified and better understood. The "NoLap" study (7) suggested that a cohort of these patients who didn't have a laparotomy might in retrospect have had a better chance of survival if they had. To investigate this, patient factors will be analysed and patterns that significantly influence mortality will be determined. Results will provide insights into the different patient groups and improve our

understanding of their risk of death, with or without surgery. This will enable clinicians to more intelligently advise patients and their relatives on risks of laparotomy against alternative management.

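### The primary mortality rates are promised for all patients with an intestinal emergency, but cohort entry requires a full set of vital signs and bloods on the day of admission, which those rates do not need

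*Protocol*

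**What the plan says.** Eligibility is set in the Synopsis (Section 2) and repeated in Section 7.4. Besides a coded acute intestinal condition and an age limit, a patient must satisfy two data conditions: "Have at least one full set of vital signs recorded on the day of admission" and "Have at least one full set of routine blood tests recorded on the day of admission".

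Section 7.4 also fixes the order. Coded patients are found first, and then: "Once patients have been identified, they will be screened against the inclusion/exclusion criteria".

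The Synopsis gives the primary endpoint as "Mortality risk for each treatment group". Section 7.2 lists the primary outcomes as length of stay and in-hospital, 30-day and 1-year mortality. Section 10.2 forms the treatment groups from diagnosis and procedure codes, and Section 9.1 takes the outcomes from linked data sets.

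The population promised is wider than the one screened in. Section 4.2 speaks of "providing information on the 30-day and 1-year mortality for all patients with an intestinal emergency admitted to our hospital", Section 4.1 of "outcomes for ALL patients admitted with an intestinal emergency", and the first objective in Section 6.2 is to "Identify all patients with a condition that would qualify them for emergency abdominal surgery".

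On missing data, Section 10.2 reports that in 2018 "clinical data within 24h of admission was almost fully complete" for more than 97% of admissions. It undertakes to test whether dropping admissions with missing data introduces bias.

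**The concern.** A crude mortality rate for a treatment group needs a denominator from codes and a numerator from deaths. Vital signs and bloods enter only the early warning scores, the description of patients and the risk models (Sections 10.1 and 10.2). Making them a condition of entry to the whole cohort removes patients from the primary rates for a reason unrelated to those rates. Length of stay, also a primary outcome, is affected in the same way.

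This does harm only if the patients removed differ in risk from those kept. Whether an early full set is recorded may depend on how ill the patient is or which path is taken. The documents do not show who is lost, so this is a possibility and not a demonstrated bias. The rates are the study's main output and are meant to inform patients and relatives choosing between treatments. If availability differs between groups, the gap between groups is more exposed than the overall rate.

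**Working it through.** **Inputs (Protocol Section 8, 2018 pilot).** 901 patients, of whom 530 had surgery, so 901 − 530 = 371 did not. In-hospital deaths: 23 with surgery and 28 without, 51 in total.

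**The plan's own figures reproduce.** 901 × 6.5 = 5,856.5 (stated: over 5,800). 530 × 6.5 = 3,445 (stated: over 3,400). 23/530 = 4.34% (stated 4.3%). 28/371 = 7.55% (stated 7.6%, which differs only in the last rounded digit). Overall 51/901 = 5.66%. Gap, no surgery minus surgery: 7.55 − 4.34 = 3.21 points.

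**Does the 97% figure bound the loss?** No. It counts data that are nearly complete within 24 hours, whereas the criterion asks for a full set on the day of admission. If that means the calendar day, a late-evening admission can meet the first and fail the second. The 3% used below is therefore an assumption, not a ceiling.

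**Overall rate.** Let q be the mortality of those lost; q is not in the documents. The protocol does not say whether 901 is counted before or after screening, so both cases are shown.

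- 901 after screening: lost = 901/0.97 − 901 = 27.9; rate in all coded patients = (51 + 27.9q)/928.9.
- 901 before screening: lost = 0.03 × 901 = 27.0; rate in the screened cohort = (51 − 27.0q)/874.0.

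| q | All coded patients, if 901 is after screening | Screened cohort, if 901 is before screening |
|---|---|---|
| 0% | 5.49% | 5.84% |
| 5.7% (same as the rest) | 5.66% | 5.66% |
| 20% | 6.09% | 5.22% |
| 50% | 6.99% | 4.29% |

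**Gap between groups, 901 after screening (gap in all coded patients).**

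| Where the 27.9 fall | Formula | q = 0% | q = 20% | q = 50% |
|---|---|---|---|---|
| All no surgery | (28 + 27.9q)/398.9 − 4.34% | 2.68 | 4.08 | 6.17 |
| All surgery | 7.55% − (23 + 27.9q)/557.9 | 3.42 | 2.43 | 0.93 |
| Proportional, equal q | 0.97 × 3.21 | 3.11 | 3.11 | 3.11 |

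**Gap between groups, 901 before screening (gap in the screened cohort).** Here 371 − 27.0 = 344.0 and 530 − 27.0 = 503.0.

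- All lost from no surgery, (28 − 27.0q)/344.0 − 4.34%: 3.80 points at q = 0% and −0.13 at q = 50%.
- All lost from surgery, 7.55% − (23 − 27.0q)/503.0: 2.97 points at q = 0% and 5.66 at q = 50%.
- Proportional with equal q, 3.21/0.97: 3.31 points.

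**A less extreme case.** If the share lost is f, and those lost die at RR times the retained rate, the all-patient rate is retained rate × [(1 − f) + f × RR]. With 7.55% as the retained no-surgery rate and f = 3%, RR = 1 gives 7.55%, RR = 2 gives 7.77% and RR = 5 gives 7.55 × 1.12 = 8.45%. For scale, the 95% confidence half-width with 371 × 6.5 = 2,411 patients is 1.96 × √(0.0755 × 0.9245/2,411) = 1.05 points. With f = 10% and RR = 5 the rate is 7.55 × 1.40 = 10.57%.

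**The case against.** The best defence has four parts.

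- **The word 'all' is a contrast with laparotomy-only audit.** Read literally it would also clash with the age limit and the maternity exclusion, to which nobody objects. This is partly right, and the background wording is loose. But those limits define a clinical population, while the data conditions depend on what happened to be recorded.
- **The protocol already promises a bias check, and its details may sit in a statistical analysis plan.** The check is welcome, and its method can be left to that plan. Eligibility, however, is fixed in the protocol. It is not clear that the check reaches patients removed at entry, and whatever it finds, the reported rates remain those of the selected cohort.
- **One cohort for rates, description and models is a defensible choice.** Objective 2 pairs mortality with clinical characteristics, and results are to be compared with P-POSSUM. This is a fair reason to keep the requirement for those analyses, but not for the crude rates.
- **The figures are scenarios.** This stands. The ends of the gap range need every lost patient to be in one group and half of them, or none, to die. They describe in-hospital deaths in one pilot year. A shift of 0.9 points at fivefold mortality is within the confidence half-width.

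Nor does any passage document unequal recording of vital signs or bloods. Section 4.3 reports that in the earlier UK cohort study patients without surgery less often had a CT-informed decision (67% vs 82%) or a risk assessment (24% vs 37%). Those are different items and show only that equal recording cannot be taken for granted.

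**Conclusion.** The point holds. Following the protocol as written selects the primary mortality rates on the availability of data that those rates do not use, and no analysis of the unscreened coded cohort is described. The population reported would not be the one promised in Section 4.2.

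The numerical effect cannot be derived from the documents and may be small. It is nil for the overall rate if those lost resemble the rest. At an assumed 3% loss with 0% to 50% mortality among those lost, the overall in-hospital rate of 5.7% would correspond to 5.5% to 7.0% in all coded patients if 901 is the post-screening count. If 901 is the pre-screening count, the screened cohort would show 5.8% down to 4.3%. The range of 0.9 to 6.2 points for the gap belongs to the post-screening reading only; on the other reading the screened gap would run from about −0.1 to 5.7 points. No direction of bias is claimed. The change should be made, because it is cheap and removes the question, but the study does not fail without it.

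**What to change.** - Report the primary mortality rates, and length of stay, by treatment group in all code-eligible first admissions.
- Apply the vital-sign and blood-test conditions only to the analyses that use those data: the early warning score description and the risk models, and the P-POSSUM comparison where it needs them.
- State one time window, reconciling the day of admission in Sections 2 and 7.4 with the 24 hours in Section 10.2.
- As the bias check already promised in Section 10.2, report the number, treatment group and mortality of coded patients who fail each data condition.

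The cost is protocol wording. Section 7.4 already identifies every coded patient before screening, so no new identification step is needed. The one drawback is that the rates and the risk models will have slightly different denominators, which the report should state.
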